## 3. STUDY DESIGN

This is a Phase 2B two-site, open-label, nonrandomized 24-week study of the efficacy and safety of vismodegib (150 mg PO daily) in subjects with high risk and/or locally advanced basal cell carcinoma. A total of 36 subjects with infiltrative/morpheaform, nodular, or superficial BCC will be enrolled in the study. Each subtype group will have a minimum of 10 subjects. No group will have more than 16 subjects.

At Treatment Initiation Visit (Baseline/Day 1), eligible subjects will begin a 24-week treatment regimen with vismodegib 150 mg daily. Clinical assessments will be performed every 4 weeks during treatment. Intra-treatment tissue histopathologic evaluation will be conducted at Week 12. Subjects will be eligible to discontinue treatment early and enter the Observation period if there is no histologic evidence of tumor on Week 12 pathology specimens. Post-treatment histopathologic evaluation will be performed at Week 24 (End of Treatment visit). Subjects will be eligible to enter the Observation period in lieu of surgery if their target lesion displays complete histologic response on biopsy specimens obtained at Week 24 visit. For subjects with histologic evidence of disease on pathology at Week 24 visit, surgical excision or Mohs surgery on the target lesion will be performed within 4 weeks of the last dose of study drug. Patient Reported Outcomes (PRO) data will be collected at baseline visit, during treatment, end of treatment/early termination visit, surgical visit, and study exit (post-surgery) visit, and at first Observation period visit (when applicable) Safety assessments including adverse event (AE) monitoring and concomitant medications will be performed at each visit.

The rationale for using 24-week treatment schedule was based on previous data from pilot studies. Data from a previous trial of 33 subjects with advanced BCC, demonstrated that 94% (17/18) of responders responded by 24-weeks. (Von Hoff et al 2009) In non-responders, treatment beyond 24 weeks may unnecessarily endanger the patient and allow their basal cell skin cancer to progress potentially negatively affecting clinical outcome.

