### **6.1.2 Treatment Initiation Visit (Baseline/Day 1)**

The objective of this visit is to ensure that subjects who will enter the study continue to meet all inclusion and exclusion criteria and to perform baseline evaluations of the biopsy-confirmed BCC target lesion site.

For subjects with >1 histologically-confirmed BCC identified at Pre-study Screening Visit, target lesion assignment for primary endpoint analysis is described in Section 9.2.1 Target lesion assignment.

The study visit should occur within 4 weeks of Pre-study Screening visit.

The following procedures will be performed at Treatment Initiation Visit (Baseline/Day 1) after confirmation that the subject has met all inclusion criteria and has no exclusion criteria present:

- Assessment of any changes (deletions, additions, or dose modifications) to medications.
- Complete physical examination including general appearance, skin exam, and visual inspection of target lesion.
- Vital signs (BP; heart or pulse rate; and oral, tympanic, or temporal temperature).
- Weight and height measurements.
- Urine pregnancy test ( $\alpha$ -hCG) for women who are of childbearing potential.
- Photography and measurement of target lesion(s) with ruler visible in photographic field
- Template map drawing of clinically evident tumor margins and local landmarks using a permanent marker on a clear plastic overlay.
- Complete an evaluation of target tumor, including:
  - Tumor measurement/dimensions Photograph target lesion
  - Adverse Event (AE) Monitoring.
- Subjects will complete the Patient Reported Outcomes (PRO) questionnaire: SKINDEX-16 to obtain baseline information. (Appendix 6)
- Dispense study drug bottles.
- Provide appropriate training and specific written instructions for study drug (capsules) self-administer by subject.

- Observe subject administer first dose of study drug (on Day 1 only)
- Review subject diary and instructions on completion for daily dosing/drug accountability. The subject will be instructed to begin data diary recording at home.
- Reminder to use effective measures to avoid pregnancy
- Subject will be given written instructions for adverse event monitoring, measures to avoid pregnancy and avoiding of blood production products (Appendix 7.)

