### 6.1.2 Interval Visits

The objectives of these interval visits are to provide a systematic and objective evaluation of the target tumor, and to monitor subject safety while ensuring continued compliance with study procedures. Every attempt should be made to have individual subject assessments performed by the same physician (investigator or equally qualified physician listed on FDA form 1572), preferably on the same day of the week for each visit.

The following procedures will be performed at all visits during treatment:

- Assessment of any changes (deletions, additions, or dose modifications) to medications.
- Complete physical examination including general appearance, skin exam, and visual inspection of target lesion(s).
- Vital signs (BP; heart or pulse rate; and oral, tympanic, or temporal temperature).
- Weight and height measurements.
- Urine pregnancy test ( $\alpha$ -hCG) only for women who are of childbearing potential.
- laboratory evaluation to evaluate abnormalities in hematocrit/platelet counts, renal or hepatic function and electrolytes if deemed necessary by the investigator.
- Photography and measurement of target lesion with ruler visible in photographic field
- Template map drawing of clinically evident tumor margins and local landmarks using a permanent marker on a clear plastic overlay.
- Adverse Event (AE) Monitoring.
- Review subject dosing diary and conduct accountability of used and unused study drug returned by the subject to determine study drug dosing regimen compliance.
- Collect unused study drug and re-dispense study drug
- Observe subject administer doses of study drug and document in the dosing diary.
- Clinical Response Evaluation by investigator (See below Section 6.2.2, Clinical response evaluation of target lesion for instructions)
- Reminder to use effective measures to avoid pregnancy
- Remind subjects to bring all unused drug supplies with them to their next scheduled visit.

Week 8, 16, and 24, Surgery Visit, Study Exit Visit (Post-Surgery Visit): PRO questionnaires will be performed by the subject (SKINDEX-16 and Functional Assessment of Cancer Therapy – General (FACT-G). (Appendix 7 and 9.)

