##### 9.3.2.3 **Patient Reported Outcomes/Quality of Life**

Evaluation of patient reported outcome (PRO) measures before, during 24 weeks of treatment with vismodegib through SKINDEX-16 and FACT-G questionnaires. (See Appendix VI and VIII.)

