#### 9.3.3.2.3 **Patient Reported Outcomes**

Quality of life (QoL) during study participation and patient impression of adverse effect tolerability will be assessed.

QoL will be assessed using patient reported outcomes (PRO) questionnaires at Baseline, Week 8, Week 16, and Week 24 study visit/End of treatment visit using the following validated measures:

- FACT-G (v. 4), Functional Assessment of Cancer Therapy-General (Appendix VIII)
- Skindex-16, a quality-of-life measure for patients with skin disease (Appendix VI.)

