## 14.6

## APPENDIX 6: STUDY PROCEDURES FLOWCHART

**Subjects with partial response or stable disease after 24 weeks of treatment and undergo surgical excision within 4 weeks of last dose of study drug.**

	Pre-study Screening Visit	Treatment Initiation Visit	Visit 2	Visit 3	Visit 4	Visit 5	Visit 6	Visit 7	Visit 8	Study Exit Visit 
	Day 0	Baseline / Day 1	Week 4	Week 8	Week 12	Week 16	Week 20	Week 24	Surgery Visit	30 days after surgery
Procedure										
Sign & Date Informed Consent	X									
Collect Medical History	X									
Review Inclusion/Exclusion Criteria	X	X								
Review Concomitant medications	X	X	X	X	X	X	X	X	X	X
Review Adverse Events (AEs)		X	X	X	X	X	X	X	X	X
Physical exam	X	X	X	X	X	X	X	X	X	X
Vital signs	X	X	X	X	X	X	X	X	X	X
Height, weight	X	X	X	X	X	X	X	X	X	X
Target lesion identification	X									
Lesion measurement (pre-biopsy)	X									
Lesion measurement (post-biopsy)	X									
Lesion photography	X	X	X	X	X	X	X	X	X	
Tumor margins and local landmarks map	X	X	X	X	X	X	X	X	X	
Lesion punch biopsy/biopsies	X				X					
Urine Pregnancy Test	X 	X	X	X	X	X	X	X	X	X
CMP/CBC Tests	X	X 	X 	X 	X 	X 	X 	X 	X 	X 
Patient reported outcome questionnaires		X		X		X		X	X	X
Review subject diary			X	X	X	X	X	X	X	
Study drug instructions		X	X	X	X	X	X			
Reminder to use effective measures to avoid pregnancy	X	X	X	X	X	X	X	X	X	X
Administer study drug		X	X	X	X	X	X			
Pathological Evaluation (H&E)	X				X				X	
Immunohistochemical Evaluation	X				X				X	
Pathologic Slide Photography	X				X				X	
Breslow depth ("invasion index")	X				X				X	
Perform Mohs Surgery on target lesion(s)									X	
Assess/treat post-surgical tumor area										X
Assess Adverse Events (AEs)		X	X	X	X	X	X	X	X	X

### Subjects with complete clinical response and complete histologic response at Week 24

Description	Pre-study Screening Visit	Treatment Initiation Visit	Visit 2	Visit 3	Visit 4	Visit 5	Visit 6	Visit 7	Observation Visit 1	Observation Visit 2	Observation Visit 3	Observation Visit 4
	Day 0	Baseline / Day 1	Week 4	Week 8	Week 12	Week 16	Week 20	Week 24	Week 36	Week 48	Week 60	Week 72
Informed Consent	X											
Medical History	X											
Inclusion/Exclusion	X											
Concomitant medications	X	X	X	X	X	X	X	X	X	X	X	X
Physical exam	X	X	X	X	X	X	X	X	X	X	X	X
Vital signs	X	X	X	X	X	X	X	X	X	X	X	X
Height, weight	X	X	X	X	X	X	X	X	X	X	X	X

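### The Day 1 procedure list names SKINDEX-16 only, although the PRO endpoint and analysis sections call for both SKINDEX-16 and FACT-G before treatment

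*Combined protocol and SAP*

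**What the plan says.** The Day 1 list in Section 6.1.2 (Treatment Initiation Visit) contains one PRO item: "Subjects will complete the Patient Reported Outcomes (PRO) questionnaire: SKINDEX-16 to obtain baseline information". It is worded in the singular and names one instrument.

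The sections on endpoints and analysis ask for two:

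- Section 9.3.2.3 defines the endpoint as "Evaluation of patient reported outcome (PRO) measures before, during 24 weeks of treatment with vismodegib through SKINDEX-16 and FACT-G questionnaires".
- Section 9.3.3.2.3 states "QoL will be assessed using patient reported outcomes (PRO) questionnaires at Baseline, Week 8, Week 16, and Week 24 study visit/End of treatment visit". The measures listed for those time points are "FACT-G (v. 4), Functional Assessment of Cancer Therapy-General" and "Skindex-16, a quality-of-life measure for patients with skin disease".

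Section 3 adds "Patient Reported Outcomes (PRO) data will be collected at baseline visit, during treatment, end of treatment/early termination visit" without naming instruments. In the section on Interval Visits, both questionnaires are set for Weeks 8, 16 and 24, the Surgery Visit and the Study Exit Visit: "PRO questionnaires will be performed by the subject (SKINDEX-16 and Functional Assessment of Cancer Therapy" (the sentence goes on to complete the FACT-G title). Section 6.1.8 sets both again at the first Observation visit.

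All three flowcharts in Appendix 6 have a row "Patient reported outcome questionnaires". It is marked at Treatment Initiation, is blank at Screening, and names no instrument.

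**The concern.** Wherever else the visit text names PRO instruments, it names both. Day 1 is the only exception, so a coordinator could reasonably take the single instrument there as deliberate. Section 6.1 presents the visit sections as the detailed account of the procedures, and the flowchart only says that PRO questionnaires are due.

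The first dose is given under observation at this same visit, so a FACT-G missed on Day 1 cannot be collected later as a pre-treatment value. The study is open-label and nonrandomized and every subject receives vismodegib, so there is no untreated group to stand in for the subject's own starting score. SKINDEX-16 does not fill the gap: Section 9.3.3.2.3 presents it as a skin-disease measure and FACT-G as the general cancer-therapy measure. FACT-G asks about energy and nausea (Appendix 9), and Section 1.3 lists fatigue and nausea among the most common adverse events. The general questionnaire is thus the one more likely to pick up tolerability, and it is the one left off Day 1.

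**Working it through.** The plan states no figure to reproduce. The check sets the schedule in Section 9.3.3.2.3 against the instruments named in the visit text of Section 6.1.

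| Time point | SKINDEX-16: analysis section / visit text | FACT-G: analysis section / visit text |
|---|---|---|
| Baseline (Day 1) | yes / yes | yes / **no** |
| Week 8 | yes / yes | yes / yes |
| Week 16 | yes / yes | yes / yes |
| Week 24 | yes / yes | yes / yes |
| Total | 4 / 4 | 4 / 3 |

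1. *Does another pre-dose step supply FACT-G?* No. The screening procedures in Section 6.1.1 contain no PRO item, and the flowchart row is blank at Screening. FACT-G first appears by name in the section on Interval Visits, at Week 8.

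2. *Shortfall per subject.* Pre-treatment FACT-G called for: 1. Named in the Day 1 list: 0. For a subject who stays on treatment for 24 weeks, that is 1 of 4 scheduled FACT-G assessments (1/4 = 25%), and the missing one is the pre-treatment one.

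3. *Time of the first FACT-G if the list is followed.* Week 8, that is 8 × 7 = 56 days on drug, or 8/24 = 33% of the planned course.

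4. *Does the flowchart settle it?* Not fully. The label is plural, and the same row is marked at Week 8, where the visit text names both instruments. That favours the reading that both were meant at Day 1. But the row names neither, and the detailed instruction for the visit names one.

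5. *Do the appendix references help?* No. The Day 1 item points to Appendix 6 for SKINDEX-16, but Appendix 6 is the flowchart. Sections 9.3.2.3 and 9.3.3.2.3 cite Appendices VI and VIII for the two questionnaires. In the current numbering SKINDEX-16 is Appendix 7, the participant instructions are Appendix 8 and FACT-G is Appendix 9. The section on Interval Visits has the right numbers, 7 and 9.

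6. *Size of the added form.* FACT-G items in Appendix 9: 7 physical + 7 social/family + 6 emotional + 7 functional = 27.

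**The case against.** The best reply is that both instruments were plainly intended. Section 3, the two PRO subsections of Section 9 and the plural flowchart row all point the same way, so this is a drafting omission in one line and not a decision to skip FACT-G. That is probably right about intent. It does not remove the risk, because the study has two sites and the detailed text for the visit allows one of them to give SKINDEX-16 alone.

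A second reply is that the loss is modest. A reader might infer that the Day 1 score is the only reference for FACT-G on drug. The documents do not support that: FACT-G is also scheduled at the Surgery, Study Exit and first Observation visits, after treatment has ended. Those values do not replace a pre-treatment one, since by then the lesion has been treated or excised, but they are off-drug values. A reader might also infer that Week 8 answers could not be told apart from the subject's starting state at all. That is too strong. Screening medical history, ECOG status at Baseline and adverse event monitoring from Day 1 give some information on pre-existing fatigue or nausea, though none of them is a FACT-G score.

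Third, Section 9.3.3.2.3 plans no FACT-G change score and no test. This stands. It would be wrong to say that a planned change-from-baseline analysis fails. What fails is the collection of a pre-treatment value that two sections call for.

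**Conclusion.** The inconsistency is real. As written, the Day 1 list omits an instrument that Sections 9.3.2.3 and 9.3.3.2.3 require before treatment, and no other pre-dose step supplies it. A site that follows the list collects 0 of 1 pre-treatment FACT-G per subject, with the first FACT-G after 8 weeks on drug, and cannot recover the missing value.

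How many subjects this would affect cannot be read from the documents. It depends on how the two sites reconcile the list with the flowchart, and could be anywhere from 0 to all 36. The consequence is limited to one of two PRO instruments, for one of three secondary objectives, in a self-described pilot study. The primary endpoints, safety collection and the SKINDEX-16 baseline are untouched. The correction should be made because the loss is irreversible and the remedy is small.

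A reader might also infer a gap for subjects who stop at Week 12 with complete response, since their flowchart has no PRO mark at Week 12. The text does not clearly require one. Section 6.1.4 equates End of Treatment with Week 24, and that flowchart does mark PROs at Week 24 (Observation Visit 1). That point is not part of this finding.

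The conclusion assumes that nothing in the pages unavailable for this check, such as the Appendix 5 algorithms, names FACT-G before the first dose.

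**What to change.** - In the Day 1 list of Section 6.1.2, replace the PRO item with: *Before the first dose, subjects will complete SKINDEX-16 (Appendix 7) and FACT-G (Appendix 9).*
- Name both instruments in the PRO row of all three Appendix 6 flowcharts.
- In Sections 9.3.2.3 and 9.3.3.2.3, change the references to Appendix 7 for SKINDEX-16 and Appendix 9 for FACT-G.

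The cost is one 27-item questionnaire per subject at a visit that already takes place, plus the wording changes. No visit is added, and no dose or clinical rule is touched.

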### 6.1.2 Interval Visits

The objectives of these interval visits are to provide a systematic and objective evaluation of the target tumor, and to monitor subject safety while ensuring continued compliance with study procedures. Every attempt should be made to have individual subject assessments performed by the same physician (investigator or equally qualified physician listed on FDA form 1572), preferably on the same day of the week for each visit.

The following procedures will be performed at all visits during treatment:

- Assessment of any changes (deletions, additions, or dose modifications) to medications.
- Complete physical examination including general appearance, skin exam, and visual inspection of target lesion(s).
- Vital signs (BP; heart or pulse rate; and oral, tympanic, or temporal temperature).
- Weight and height measurements.
- Urine pregnancy test ( $\alpha$ -hCG) only for women who are of childbearing potential.
- laboratory evaluation to evaluate abnormalities in hematocrit/platelet counts, renal or hepatic function and electrolytes if deemed necessary by the investigator.
- Photography and measurement of target lesion with ruler visible in photographic field
- Template map drawing of clinically evident tumor margins and local landmarks using a permanent marker on a clear plastic overlay.
- Adverse Event (AE) Monitoring.
- Review subject dosing diary and conduct accountability of used and unused study drug returned by the subject to determine study drug dosing regimen compliance.
- Collect unused study drug and re-dispense study drug
- Observe subject administer doses of study drug and document in the dosing diary.
- Clinical Response Evaluation by investigator (See below Section 6.2.2, Clinical response evaluation of target lesion for instructions)
- Reminder to use effective measures to avoid pregnancy
- Remind subjects to bring all unused drug supplies with them to their next scheduled visit.

Week 8, 16, and 24, Surgery Visit, Study Exit Visit (Post-Surgery Visit): PRO questionnaires will be performed by the subject (SKINDEX-16 and Functional Assessment of Cancer Therapy – General (FACT-G). (Appendix 7 and 9.)

At week 12, Intra-treatment tissue histopathologic evaluation will be performed to assess histologic response. For subjects with apparent clinical complete response at Week 12 and no histologic evidence of disease is observed, subjects will enter the observation period and be followed clinically every 3 months up to one year (See Appendix 5, Figure 3 for more

information). Sample diagrams demonstrating the sites of screening biopsies and Week 12 biopsies for a tumor is seen in Section 6.1.3.

### 6.1.3 Intra-treatment Tissue Histopathologic Evaluation

All subjects will undergo intra-treatment Tissue Histopathologic Evaluation at Week 12 visit. For lesions that display complete clinical response, histologic presence or absence of tumor on biopsy determines whether or not the subject is eligible to end treatment early and enter the Observation period (See Appendix 5 , Figure 3). Subjects with clinical partial response or stable disease at Week 12 visit will continue treatment for the full duration of 24 week regardless of pathology on sampling biopsy (See Appendix 5, Figure 2).

#### **Tumors Exhibiting Complete Clinical Response**

For lesions that the investigator has determined to show complete clinical response at Week 12 visit, sampling biopsy will be performed at the farthest edge(s) of pre-biopsy lesion compared to location of initial punch biopsy/biopsies at Pre-study Screening Visit (See Figure 1 A). Up to three 2-mm or three 3-mm punch biopsies will be performed on the area of tumor clearance at Week 12 when possible. Tumor biopsies may comprise no more than 10% of visible lesion seen at screening visit.

[figure not shown]

Figure 1. Site of Week 12 biopsies for tumors with exhibiting complete clinical response.

For lesions that display partial clinical response or stable disease by clinical response evaluation, “Residual Tumor Assessment” and “Area of Tumor Clearance Assessment” will be performed (See Figure 2.).

[figure not shown]
#### **Residual Tumor Assessment**

A single 2-mm or 3-mm punch biopsy or up to three 2-mm or three 3-mm sampling punch biopsies will be performed on the residual tumor.

- Biopsy must be performed in area not previously biopsied.
- Biopsy of residual tumor should be performed at least 1 mm from the peripheral margin of visible or palpable lesion
- Tumor biopsies performed at Week 12 visit will comprise no more than 10% of visible lesion surface area.

**Area of Tumor Clearance Assessment**

Up to three 2-mm or three 3-mm punch biopsies will be performed on the area of tumor clearance at Week 12 when possible.

**Figure 2. Site of Biopsies at Pre-study Screening Visit and Week 12 visit for tumors exhibiting clinical partial response or stable disease.**

**6.1.4 End of Treatment visit (Week 24)**

Any unused study drug will be collected.

After 24 weeks of treatment, all subjects will undergo sampling biopsy/biopsies. If residual histologic disease is detected, surgical excision will be performed within 4 weeks of last dose of study drug. If no histologic evidence of disease is observed, subjects will enter the observation period and be followed clinically every 3 months up to one year. (See Appendix 5, Figure 1 and Figure 2.)

Biopsies at Week 24 visit will be performed in similar manner as performed at the Week 12 visit.

For lesions that the investigator has determined to show complete clinical response at Week 24 visit, sampling biopsy will be performed at the farthest edge(s) of pre-biopsy lesion compared to location of initial punch biopsy/biopsies at Pre-study Screening Visit and sites of biopsies performed at Week 24 visit (See Figure 3). Up to three 2-mm or three 3-mm punch biopsies will be performed on the area of tumor clearance at Week 24 when possible. Tumor biopsies may comprise no more than 10% of visible lesion seen at screening visit.

[figure not shown]

Figure 3. Site of biopsies for tumors displaying clinical complete response at Week 24 visit.

For lesions that display partial clinical response or stable disease by clinical response evaluation, “Residual Tumor Assessment” and “Area of Tumor Clearance Assessment” will be performed (See Figure 4)

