### **Residual Tumor Assessment**

A single 2-mm or 3-mm punch biopsy or up to three 2-mm or three 3-mm sampling punch biopsies will be performed on the residual tumor.

- Biopsy must be performed in area not previously biopsied.
- Biopsy of residual tumor should be performed at least 1 mm from the peripheral margin of visible or palpable lesion
- Tumor biopsies performed at Week 24 visit will comprise no more than 10% of visible lesion surface area.

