### **Area of Tumor Clearance Assessment**

Up to three 2-mm or three 3-mm punch biopsies will be performed on the area of tumor clearance at Week 24 when possible.

[figure not shown]

Figure 4. Site of biopsies for tumors that display partial response or stable disease at Week 24 visit.

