#### 9.3.1.2 **Histologic response (at Week 12 and Week 24/Surgical Visit)**

- **Residual tumor**
  - Evidence of any histologic change in residual tumor tissue compared to pre-treatment biopsy specimens
  - Estimate of changes in cellular density and composition at Week 12 and Week 24/Surgical Visit
- **Area of Tumor Clearance**
  - Assessment of histologic clearance in areas of apparent clinical tumor clearance at Week 12 and Week 24, and/or Surgical Visit
- Comparison of deepest “invasion index” on biopsy specimen, at Week 12 biopsy, and “debulking” specimen or “tumor margins” specimen” at Surgery visit
- Histologic subtypes observed on pathologic specimens (Screening visit and Week 12 and Surgical excision specimen) Location and depth of specific tumor cells of each histologic subtype on biopsy, week 12 biopsy, and Surgical excision specimens
- Percentage of each histologic subtype in tumor specimen on biopsy, Week 12 biopsy and surgical excision specimens

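### The Week 24 biopsy-site rule refers to Week 24 itself instead of Week 12, so no text keeps complete-response or clearance-area punches off sites already punched at Week 12

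*Combined protocol and SAP*

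**What the plan says.** Every subject is biopsied during treatment: "All subjects will undergo intra-treatment Tissue Histopathologic Evaluation at Week 12 visit" (section 6.1.3). For a lesion in complete clinical response at that visit, "sampling biopsy will be performed at the farthest edge(s) of pre-biopsy lesion compared to location of initial punch biopsy/biopsies at Pre-study Screening Visit".

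Section 6.1.4 then governs the end of treatment. In general, "Biopsies at Week 24 visit will be performed in similar manner as performed at the Week 12 visit". For a lesion in complete clinical response at Week 24 the farthest-edge rule is repeated, but the reference points become the initial punches at the "Pre-study Screening Visit and sites of biopsies performed at Week 24 visit". The sentence points to Figure 3.

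For lesions in partial response or with stable disease there are two kinds of punch at each visit. The residual-tumor punches carry a protective sentence, "Biopsy must be performed in area not previously biopsied". The clearance-area punches carry only a number and a size: "Up to three 2-mm or three 3-mm punch biopsies will be performed on the area of tumor clearance at Week 24 when possible".

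The Week 24 result is used twice. It decides the next step: "If no histologic evidence of disease is observed, subjects will enter the observation period and be followed clinically every 3 months up to one year"; otherwise the lesion is excised. It is also listed among the primary endpoints in section 9.3.1.2: "Assessment of histologic clearance in areas of apparent clinical tumor clearance at Week 12 and Week 24, and/or Surgical Visit".

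**The concern.** The second reference point in the Week 24 rule is self-referential. Week 12 is the only earlier on-treatment biopsy visit, and the sentence does not name it. The protocol evidently recognizes that earlier punch sites should be avoided, because it says so for residual tumor. It does not say so for the punches that establish clearance.

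Clearance is where the omission matters. If a Week 12 punch removed tumor and the Week 24 punch falls on the same spot, a tumor-free specimen may reflect the earlier punch and not the drug. This error runs mainly one way, toward apparent clearance. It would enter the histologic response that section 9.3.3.1.2 analyzes overall and by subtype, and it could place a subject with residual tumor in the observation period.

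**Working it through.** The plan states no figure on this point, so the check sets the site rules side by side and then traces which lesions they reach.

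**Site rules by type of punch**

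| Punch | Reference for siting | Earlier sites excluded? |
|---|---|---|
| Week 12, complete clinical response (6.1.3) | Farthest edge(s) from the screening punch | Screening sites, by distance |
| Week 24, complete clinical response (6.1.4) | Farthest edge(s) from the screening punch and from Week 24 sites | Screening sites only; Week 12 not named |
| Residual tumor, Week 12 and Week 24 | At least 1 mm inside the margin | Yes, stated |
| Clearance area, Week 12 and Week 24 | None | Not stated |

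The procedures flowchart (Appendix 6) does not settle the matter. Its punch-biopsy row is marked at screening and Week 12 only.

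**Which lesions are exposed at Week 24**

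1. Clinically clear and histologically negative at Week 12. These go to observation (sections 6.1.2 and 6.1.3) and have no Week 24 treatment biopsy. Not exposed.
2. Clinically clear but histologically positive at Week 12. These do not qualify to end treatment early. Their Week 12 punches were placed by distance from the screening punch, and the only usable reference in the Week 24 sentence is that same screening punch. Most exposed, and known to have had tumor at the Week 12 site.
3. Partial response or stable disease at Week 12, complete clinical response by Week 24. Their Week 12 punches followed the residual-tumor and clearance-area rules, not the farthest-edge rule. The sites need not coincide, but nothing excludes it.
4. Partial response or stable disease at Week 24. Residual-tumor punches are protected; clearance-area punches are not.

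**What one lesion is worth.** Section 3 sets 10 to 16 subjects per subtype group. If all of a group count in the denominator, one misclassified lesion moves that group's rate by 1/10 = 10 percentage points, or 1/16 = 6 points. This measures sensitivity; it does not estimate bias.

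**Illustration of overlap, under assumed random placement.** Take a round 10 mm lesion with a central screening punch and one 3-mm edge punch at each visit.

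- Lesion area: π × 5² = 78.54 mm². The 10% cap is 7.85 mm². One 3-mm punch is π × 1.5² = 7.07 mm², so one fits.
- Punch centers lie on a circle of radius 5 − 1.5 = 3.5 mm.
- Any contact: centers less than 3 mm apart, so angle < 2·arcsin(3/7) = 50.8°. Probability 2 × 50.8/360 = 28%.
- More than half the punch overlapped: centers within about 1.21 mm, so angle < 2·arcsin(1.21/7) = 19.9°. Probability 2 × 19.9/360 = 11%.
- With centers placed uniformly over the lesion instead, any contact has probability about 20% (one 2-mm punch at each visit) to 47% (one 3-mm). In a 20 mm lesion the range is about 5% (one 2-mm Week 12 punch) to 28% (three 3-mm).

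The results swing with the assumption. They are probabilities of overlap, not of a false-negative reading.

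**The case against.** The strongest reply is that no competent reader would be misled. The Week 24 sentence adds a second set of sites to stay away from. It cannot mean Week 24, and Week 12 is the only candidate. The Week 12 manner of sampling, which section 6.1.4 carries forward, already moves away from earlier punches. The sentence also refers to Figure 3, captioned for exactly these lesions. That figure is not shown in the copy reviewed and may mark the Week 12 sites. The most exposed group is narrow, clearance is one of many components under the primary endpoints of a self-described pilot, and sampling limited to 10% of a lesion can miss tumor anyway. Observation includes an examination every 3 months, with biopsy of any suspected recurrence.

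Much of this stands. Most investigators probably would read Week 12. A reader might infer the stronger claim that the rule sends both visits to the same edge. The text does not support that: the same-edge result appears only if the faulty clause is ignored, the rule speaks of edges in the plural, and up to three screening punches may define the distance. Nor can the overlap percentages be read as the share of false clearances. They count any contact between punches under an assumed placement, and the documents give no false-negative rate for a re-sampled site.

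What does not fall away is the gap itself. The clearance-area punches have no avoidance wording to reinterpret, and a charitable reading of the complete-response sentence is still left to each investigator at two sites. Follow-up may find missed tumor later, but would not by itself correct the Week 24 endpoint.

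**Conclusion.** The point holds as a wording error in an operative sampling rule, together with a gap in coverage. The Week 24 sentence names the wrong visit, and no text protects Week 12 sites for complete-response or clearance-area punches. If a Week 12 site is re-sampled, histologic clearance can be overstated and the choice between observation and surgery affected. The concern is mainly for lesions clinically clear but histologically positive at Week 12.

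The likely direction is upward. The size cannot be computed: the documents give neither the expected number of such lesions, nor how often sites would coincide in practice, nor how often a re-sampled site reads falsely negative. The conclusion assumes that Figure 3 does not already show Week 12 sites as excluded. If it does, the text still needs to be made to agree with it, and the practical risk is smaller. A reader might go further and infer that the trial's Week 24 histologic results are biased by a known amount; the documents do not support that.

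**What to change.** Three changes in one amendment:

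1. In section 6.1.4, reconcile the complete-response sentence with the Week 12 rule in 6.1.3, the Residual Tumor Assessment text and Figure 3, so that it names the Week 12 sites as the second set to stay away from.
2. Repeat the existing sentence "Biopsy must be performed in area not previously biopsied" for complete-response punches and under Area of Tumor Clearance Assessment.
3. Have Week 12 punch sites marked on the template map already drawn at that visit. This step is needed because the map is specified to show tumor margins and landmarks, not punch sites, and photographs before and after biopsy are specified only at screening (section 6.2.4). A lesion in complete clinical response has no visible margin from which to find the earlier punches.

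The cost is one corrected visit number, one repeated sentence and a mark on an existing form, with no extra biopsies or visits. The small downside is less choice of site in the smallest lesions.
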